The ultimate goal of the proposed study is not to reduce the experience of social stress at the population level *per se*, but to understand whether these types of experiences have a deleterious impact on CKD outcomes and/or physiological processes and design psychological interventions with these stressors in mind. In this respect, experiences of racism and other social stressors are comparable to other forms of chronic (job strain, caregiving) or uncontrollable (breast cancer, loss, trauma) stress for which psychosocial treatments have been established. Current interventions to delay progression of CKD focus primarily on nutrition, lifestyle, and medical management of blood pressure and glucose and albuminuria. The proposed project establishes the need to determine whether stress reduction might also be an important target for future intervention.

II. Goals/Aims:

This proof of concept study will recruit a sample of 100 African American patients, 80 with diagnosed CKD with equal numbers across stages 2, 3A, 3B, and 4 and 20 with no CKD diagnosis, to determine whether discriminatory stressors are an important risk factor for CKD-related physiological processes and kidney functioning in this understudied population (see Table 1).

Table 1. Stages of CKD

Stage	Description	Estimated GFR (mL per minute per 1.73 m ²)
1	Kidney damage with normal or increased GFR	≥ 90
2	Mild CKD	60 - 89
3A	Moderate CKD	45 - 59
3B	Moderate CKD	30 - 44
4	Severe CKD	15 - 29
5	Kidney failure	<15 (or dialysis)

Drawing from a recent heuristic model by Bruce et al.,¹⁹ it is theorized that the relationship between stress related to discrimination and kidney outcomes is mediated by inflammatory cytokines and blood pressure dysregulation. Further, because discriminatory

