learn more about the study. If he/she is interested in participating, he/she will have the opportunity to review specific participation requirements at their next appointment, or upon next visit to the clinic. Participants will provide consent and be enrolled in person. The second tier of participant recruitment will consist of the project coordinator using the potential participant list to call individuals who are patients in the clinic and potentially eligible for the study, and inform them about the opportunity to participate in the study. Those individuals who are interested in participating will have an opportunity to review specific participation requirements at their next appointment, or upon visiting the clinic, and will provide consent and be enrolled in person. Next, the project coordinator will provide clinic staff with a recruitment postcard (see attached example) which will be included in potential participant's exit material after their doctor's visit. The postcard provides study information, and instructs patients to contact study staff through email or phone calls if they are interested in the study. Finally, study recruitment flyers will be placed throughout the clinic (see attached for flyer example) and remain in the clinic until the conclusion of the study. The flyer provides preliminary information about the study, and instructs patients who may be interested in participating to call or email the project coordinator for more information. The project coordinator will provide further information about the study; those individuals who are interested in participating will have an opportunity to provide consent and be enrolled in person at their next appointment time. We will continue this quota sampling and recruitment process until we have enrolled 20 participants in each of the five categories: no CKD diagnosis and CKD diagnosis stage 2, 3A, 3B, and 4.

Study enrollment will occur in person within the clinic. The previously mailed letter, phone call and posted flyers will serve as an initial introduction to the study. Upon study enrollment, we will work with clinic staff to verify stage of CKD diagnosis (where applicable) to ensure that we are achieving the desired quotas. We will continue recruitment until the desired sample is achieved.

E. Field Methods

Data Collection Overview

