instructed to bring a list of current medications and to indicate any medical conditions on a patient history form (see attached). We will document these medications and any reported medical conditions (in addition to any reported conditions on participants' medical charts), and control for them in analyses.

Participants will first provide height and weight measurements, a urine sample, and baseline blood pressure testing. A research nurse will insert an intravenous catheter, and take an initial blood draw (up to 4 mL to measure A1C and up to 4 mL to measure creatinine) and allow for a 30-minute habituation period so that the participant adapts to the indwelling catheter. Once the participant has adapted, participants will be asked to rate their level of distress using the Subjective Units of Distress Scale³² (SUDS). Participants will be asked to rate their level of distress on a linear scale of 0 to 100, with 100 being the highest. The nurse will take a blood draw (up to 6mL to measure inflammatory biomarkers and up to 4mL to measure eGFR).

Figure 2. Day 2 Data Collection, Experimental Manipulation

Figure 2. Day 2 Data Collection, Experimental Manipulation

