manipulation task. The audience will be trained to remain neutral during the task, told to not show empathy and not to smile at any time during the test. Observers have not yet been identified, however once determined, the individuals serving as observers will obtain a CITI certification, and study staff will submit observer credentialing as amendment modification to the protocol. The project coordinator will also remain in the room while participants recall each designated stressful experience. Blood pressure readings will be taken every 1 minute during the participant's preparation time and the actual recall task. The participant will be expected to use the entire three minutes for recall in each exercise; the project coordinator will cue the participant to continue until the 3-minute mark via standardized prompts from a script. Participants will be asked to rate their level of distress caused by the stressful event using an adapted version of Cooper's racism recall scale.³⁴ and again rate their level of distress on a linear scale (0 to 100) using the SUDS³². Participants will undergo a 45-minute recovery period after the first recall task; blood pressure readings will be taken every 5 minutes during this period. Immediately following the first 45-minutes of recovery, participants will provide a third blood draw (6 mL). Participants will undergo another 45-minutes of recovery, and provide and one final blood draw (6 mL) at the conclusion of the recovery period.

Over the course of the study, participants will provide 3, 4 mL samples of blood and 3, 6mL samples of blood. A total of up to 30 mL may be taken over the course of the study. The project coordinator will debrief participants on the purpose of the experimental manipulation and common reactions to it. Participants will also be debriefed on the entire experimental manipulation experience, including the audience's purpose. Participants will be paid \$150 at the conclusion of Day 2 (\$50 for return of ABPM and \$100 for completion of experimental manipulation). The experimental protocol along with data time points are outlined in Figure 2.

Data Sources

Participants will be asked to provide data from the following sources:

- **Cross-sectional survey data** that are provided by completing the CAPI (see attached)
- **Medical chart data**, used only to verify their last eGFR in order to achieve equal numbers of participants by study stage/CKD diagnosis

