- v. **Kidney Functioning.** We will use eGFR to measure kidney function using the abbreviated Modification of Diet in Renal Disease study equation as is recommended.^{41,42} Thus, we will measure serum creatinine from a baseline blood draw. Along with age, gender, and race, this information will be used in an online GFR calculator that is made available by the National Kidney Disease Education Program. At baseline, participants will provide a urine specimen so that we can determine the protein/creatinine ratio.⁴²
- vi. **Covariates.** Covariates to be assessed include behavioral factors (e.g., smoking, alcohol use, unhealthy diet, physical activity), socio-economic factors (e.g., health insurance status, income, and education), psychosocial factors (e.g., depression, quality of life), comorbidities (e.g., health conditions, medications, blood glucose control measured via HbA1C, and ApoL1 status), and demographics such as age, sex, and body mass index. Depressive symptoms will be assessed with the Beck Depression Inventory (BDI),⁶⁰ which is a self-administered 21-item scale that has acceptable sensitivity and specificity with regards to a clinical diagnosis of depression, and also provides a continuous measure of depressive symptoms. We will also assess previous self-reported diagnosis of major depression and previous use of antidepressant medications in addition to kidney disease quality of life.⁶¹
- vii. **Acute vs. Discriminatory Stress Experimental Manipulation.** At the end of the rest period, patients will be asked to recall a personally relevant stressor, involving a general or racism-related stressful experience. Participants will be randomized into one of the two recall groups. In the general stress protocol, participants will be asked to give a detailed account of a stressful experience (non-racial in nature) in which they felt so upset, angry, or annoyed at the time that talking about it during the clinic visit might still be upsetting to them. In the racism recall protocol, patients will be asked to provide a detailed account of a stressful experience involving *racism*-- one where they were so upset/angry/annoyed at the time that talking about it during their visit might still be upsetting to them. In both scenarios, patients will be asked to visualize the situation and recall the details of what happened, including: 1) where they were; 2) who else was there; 3) what was said and done (by the participant and by any other individuals present

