The first hypothesis is a meditational hypothesis. We recognize that Baron and Kenny⁶⁴ methods for testing mediation are among the most widely cited, but also acknowledge that there are convincing critiques of this approach such as the requirement that there be a significant direct effect of the independent variable on the outcome in order to proceed with meditational analyses.^{65,66} Thus, we will use meditational methods proposed by Zhao et al⁶⁵ that entail first running the Preacher and Hayes⁶⁷ SPSS syntax commands to generate “bootstrap” results for the indirect effect of chronic discriminatory stress (controlling for general stress) on each of the two kidney outcomes (eGFR and proteinuria) through the inflammatory pathway as measured by each of the proposed biomarkers (MCP-1, IL-6, suPAR). Bootstrapping relaxes assumptions about the shape of the sampling distribution of the indirect effect over repeated sampling from the population.⁶⁸ These analyses will control for relevant covariates. Next we will classify the type of mediation using the Zhao et al typology (complementary, competitive, indirect only, direct only, or non-mediation), and proceed with interpreting the findings in light of our hypotheses. We will consider using structural equation modeling as another technique recommended to test mediation.^{69,70}

The second hypothesis will entail use of a 2X3 ANOVA to simultaneously test the main effects of stress recall (race-related or not) (discriminatory stress vs. general stress) and data collection time point (rest, stress, and recovery) on each of the outcomes (i.e., each inflammatory biomarker and blood pressure), also controlling for the relevant covariates. This test provides a form of economy by examining multiple effects at a time, while also allowing us to study the interaction between study condition and time.⁷¹

C. Statistical Power

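### The rule to control for documented conditions and medications lets CKD, and what follows from it, into Aim 1 models of kidney function

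*Combined protocol and SAP*

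**What the plan says.** Four places in the combined protocol and SAP bear on the Aim 1 covariates.

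- **Section III.E, Day 2.** Participants bring a medication list and complete a patient history form. Staff record medications and reported conditions in addition to "any reported conditions on participants' medical charts), and control for them in analyses". No aim, model or exception is named.
- **Section III.E, Research Instruments and Assessment, item vi (Covariates).** The list includes "comorbidities (e.g., health conditions, medications, blood glucose control measured via HbA1C, and ApoL1 status". It also includes quality of life, and kidney disease quality of life is to be assessed.
- **Section VIII.B.** The mediation models estimate the indirect effect of chronic discriminatory stress "on each of the two kidney outcomes (eGFR and proteinuria"). On adjustment: "These analyses will control for relevant covariates". There is no list and no selection rule.
- **Section III.E, Data Sources.** Medical chart data are "used only to verify their last eGFR in order to achieve equal numbers of participants by study stage/CKD diagnosis". This does not fit the Day 2 rule, which uses charted conditions as covariates.

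The sample is built on kidney status. Section II calls for "80 with diagnosed CKD with equal numbers across stages 2, 3A, 3B, and 4 and 20 with no CKD diagnosis", and Section III.D recruits until the study has "enrolled 20 participants in each of the five categories: no CKD diagnosis and CKD diagnosis stage 2, 3A, 3B, and 4". Table 1 defines the stages by "Estimated GFR (mL per minute per 1.73 m"), which is the quantity that serves as an Aim 1 outcome.

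**The concern.** A covariate should help to separate the effect of stress from other causes of poor kidney function. A CKD diagnosis does not do that when the outcome is eGFR, because stage is eGFR cut into bands. A complication of low GFR, or a drug started because of low GFR, is a consequence of the outcome. Holding such items fixed compares people who are already alike on kidney function, and the association under test shrinks for that reason alone. The equal-stage quotas make the overlap strong.

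Section VIII.C says the study exists to supply effect sizes for planning a larger one. A slope reduced by the choice of covariates would be carried into that plan, and hypothesis 1 could look unsupported for a reason unrelated to stress.

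**Working it through.** **The plan's own figure.** Section VIII.C gives 84% power for 8 predictors explaining 15% of variance, with N = 100 and alpha 0.05. Take f² = 0.15/0.85 = 0.1765, noncentrality 0.1765 × 100 = 17.65, and 8 and 91 degrees of freedom. The noncentral F gives 83.6%, so the figure reproduces. It is an omnibus test and does not say which 8 predictors are meant.

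**Inputs from the documents.** Five categories of 20. Bands from Table 1: stage 2, 60-89; 3A, 45-59; 3B, 30-44; 4, 15-29 (used as 60-90, 45-60, 30-45 and 15-30).

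**Assumptions.**
- The stress-eGFR correlation r is -0.2 to -0.3.
- eGFR is uniform within each band.
- The no-CKD group lies in 60-90, 75-105 or 90-120.
- Stage agrees exactly with the study's own eGFR.
- Stress is linear in eGFR plus independent noise, so the covariate is linked to stress only through eGFR and there is no confounding.

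**Formula.** Let R² be the share of eGFR variance explained by the added covariate. The unadjusted slope is r × SD. After adjustment it is r × SD × (1 − R²)/(1 − r²R²). The fraction remaining is therefore (1 − R²)/(1 − r²R²).

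**R² under the quotas, no-CKD band 60-90.**
- Category means are 75, 75, 52.5, 37.5 and 22.5, with overall mean 52.5.
- The between-category variance is (506.25 + 506.25 + 0 + 225 + 900)/5 = 427.5.
- The within-category variance is (75 + 75 + 3 × 18.75)/5 = 41.25.
- The total is 468.75 (SD 21.7), so R² for the five-level category is 427.5/468.75 = 0.912.
- For diagnosis yes/no, the difference in means is 75 − 46.875 = 28.125. The between-group variance is 0.2 × 0.8 × 28.125² = 126.56, so R² = 0.27.

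The other bands follow in the same way:

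| No-CKD band | R², diagnosis | Slope left (r = -0.2, -0.3) | R², category | Slope left (r = -0.2, -0.3) |
|---|---|---|---|---|
| 60-90 | 0.27 | 74%, 75% | 0.912 | 9%, 10% |
| 75-105 | 0.465 | 54-55%, 55-56% | 0.935 | 6-7%, 7% |
| 90-120 | 0.612 | 39-40%, 41% | 0.953 | 5%, 5% |

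Where a cell shows a range, it spans the formula and a simulation of 400,000 participants.

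**Complication or drug marker.** The same formula applies to any marker that depends on eGFR alone.
- R² = 0.10: 0.90/(1 − 0.04 × 0.10) = 0.90 at r = -0.2, and 0.90/(1 − 0.09 × 0.10) = 0.91 at r = -0.3.
- R² = 0.25: 0.75/0.99 = 0.76, and 0.75/0.9775 = 0.77.

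The documents give no value of R² for any such marker.

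**Power for one stress coefficient.** With N = 100, seven other covariates and partial r = -0.30, power is 85%. Adding diagnosis lowers it to 46-72%. Adding the five-level category lowers it to about 9-14%.

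**Not computed.** Proteinuria, the mediator-to-kidney path and the bootstrapped indirect effect.

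**The case against.** The Day 2 sentence describes data collection and names no model. The section that governs Aim 1 asks for relevant covariates, and the power statement uses 8 predictors, which could not hold every recorded drug and condition. Health conditions appear under comorbidities, which a reader may take to mean conditions other than the index disease. Data Sources limits chart use to checking eGFR. A careful analyst would probably leave the CKD label out.

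Much of this stands. A reader might infer that the plan puts CKD itself into the Aim 1 models and so removes most of the association. The documents do not support that. No section names CKD stage as a covariate, and the text allows the adjustment without requiring it. What remains is that nothing excludes it. The power example is a hypothetical whose 8 predictors are not listed, and a single CKD term would fit among them. Even without chart data, CKD and its drugs could enter through the history form and medication list.

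A reader might also infer that adjusting for any comorbidity pulls the estimate toward zero. That does not follow. The background section names diabetes and hypertension as common causes of CKD, and a condition that precedes kidney disease can be a real confounder. The calculation cannot speak to this, because it excludes confounding by construction. For proteinuria, an eGFR-based stage is not a restatement of the outcome.

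**Conclusion.** The concern holds in a limited form: the plan leaves open an adjustment that would condition on eGFR, or on its consequences, in models of kidney function. The direction of the effect is secure for CKD diagnosis and stage in eGFR models. The size is conditional. Over the assumed inputs, diagnosis leaves about 40-75% of the stress slope, stage leaves 5-10%, and one moderate consequence marker leaves about 75-90%.

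Two features of the documents bear on where in these ranges the truth lies. The inclusion criterion in Section III.C, read literally, keeps every participant's eGFR below 90, which favours the milder end for diagnosis. Objective 1, however, attaches that limit only to the 80 with CKD. The stage figure also assumes that charted stage matches the study's own eGFR; any drift between the two would lessen the loss.

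Aim 2 is not affected, because its contrast is randomised and these conditions precede randomisation. The change should be made before analysis, since it is cheap and protects the effect sizes the study is meant to produce.

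**What to change.** For Aim 1, replace the blanket rule with a covariate list fixed before analysis and justified by causal role.

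- **eGFR models:** do not use CKD diagnosis or stage as main-effect adjusters. Stage may still be used for the stage-specific exploration described in Section III.
- **Primary eGFR and proteinuria models:** leave out complications of CKD, treatments clearly given because of CKD, and kidney disease quality of life.
- **Comorbidities that plausibly precede kidney disease:** keep them as potential confounders.
- **Sensitivity models:** show results with and without hypertension, diabetes/HbA1c, BMI and drugs of ambiguous indication. The conceptual model in Section I places hypertension, diabetes and obesity on the path to kidney outcomes, and the protocol studies blood pressure as a mechanism.
- **Chart data:** reconcile the Day 2 rule with the Data Sources limit.

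The cost is a short covariate table and a one-time classification of recorded conditions and drugs, made without sight of the stress scores. The Day 2 text describes a medication list but does not mention indications, so some drugs will need judgement. Some residual confounding may remain, which the sensitivity models would help to show. Recruitment, measurement and Aim 2 do not change.

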This multi-method study will collect data from 100 African American patients (80 patients in stages 2, 3A, 3B, and 4 of CKD and 20 with no CKD diagnosis) utilizing both cross-sectional (aim 1) and experimental (aim 2) research designs (see Figure 1). The proposed methods were designed to maximize the robustness of the data while minimizing bias in study design, methodology, analysis, interpretation, and reporting. The use of validated instruments enhances the study's scientific rigor for aim 1. Random assignment to condition (for aim 2) eliminates selection bias as one potential threat to internal validity among others.²⁷ Additionally treating the two groups equivalently in terms of data collection methods and instrumentation improve internal validity by minimizing testing and instrumentation effects.²⁷ Detailed recruitment and data collection protocols further enhance the scientific rigor of the study because they ensure equal treatment of participants regardless of study condition. Finally, by intentionally studying patients along the continuum of CKD, we can explore whether there are "critical periods" in CKD progression where the relationships with stress are strongest.

Figure 1. Study Design

A. Organizational Structure

This study is funded by the National Institutes of Health (NIH), National Institute of Diabetes and Digestive and Kidney Diseases (NIDDK), and was developed by faculty in the Rollins School of Public Health. An internal medicine clinic within Emory University Hospital Midtown (at which Co-Investigator [name] currently serves as a practicing nephrologist) and the Georgia Clinical and Translational Science Alliance (GCTSA) (for which [name] serves as Co-Director) will serve as study sites. Additionally, study participants' bio-specimens will be analyzed at the Molecular Neuroimmunology Laboratory in the Department of Epidemiology at Emory. [name], who also serves as a Co-Investigator on this project, will oversee analyses of select blood samples. Outside laboratory resources will be used for processing and analyses of the remaining biospecimens.

B. Setting and location

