at that time; 4) how they felt at the time and 5) the most stressful/upsetting aspect of the experience. Patients will be given 2 minutes to prepare and 3 minutes to recount their experience for either the racial and non-racial stressful experience. This protocol has been used in other studies of African Americans³⁴ and is adapted from a widely used mental stress protocol used in studies of anger.^{62,63}

Subjective Ratings of Distress. In order to enhance the scientific rigor of this study, we will conduct a manipulation check to determine whether the experimental manipulation had its intended effect on study participants. Thus, subjective levels of distress will be measured immediately before and after the recall task. Using the Subjective Units of Distress Scale³² patients will be asked to rate their level of distress on a linear scale of 0 to 100, with 100 being the highest. Participants will also be asked to assess their level of stress directly related to reliving the stressful experience using an adapted version of Cooper's Racism Recall scale³⁴. Patients will rate their level of distress at the time of the event, and currently while thinking about the event on a linear scale of 0 to 10, with 10 being the highest.

- viii. **Inflammatory and Blood Pressure Reactivity.** Levels of inflammation will be measured at three time points during the experimental manipulation (immediately before the experimental manipulation, 45 minutes after the manipulation and 90 minutes after the manipulation) as shown in Figure 2. A description of the inflammatory markers is provided above under "Aim 1 Assessments". Systolic and Diastolic blood pressure will be assessed every 5 minutes during the rest and instruction period, every minute during the preparation and recall task, and every 5 minutes during recovery, as shown in Figure 2. Mean scores for rest, recall task, and recovery will be calculated by averaging the readings taken during each period. Blood pressure reactivity will be a change (or delta) score, calculated as the mean of the scores during the recall task minus the mean of the scores during rest, designed to represent the change in blood pressure induced by the recall task.

Overall Time Burden

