The proposed proof-of-concept study is designed to generate effect sizes to inform a future power analysis and thereby establish the legitimacy of studying this topic in a subsequent large-scale clinical trial. Thus, it is not intended to achieve the level of power to demonstrate statistical significance as is common in larger studies. Nevertheless, regarding study aim 1, if we were to perform a multiple regression with 8 predictors that explain just 15% of the variance in a given outcome, we would achieve 84% power at $\alpha=.05$ (<http://danielsoper.com/statcalc3/calc.aspx?id=9>) at N=100. For aim 2, collecting data at multiple time points is one way to maximize power. If we just consider the two study groups (intervention and control) we would achieve power of .80 to detect a medium effect (.25) at $\alpha=.05$ with a sample of just 64 participants.⁷²

IX. Training of study team

All research staff maintains a current CITI, (Group 3 Social/Behavioral) certification. Proof of certifications has been uploaded for further review. Corresponding study team members (including members of the Georgia CTSA team and nurses within the Emory University Healthcare Nephrology clinic) will undergo study-specific training.

X. Plans for monitoring the study for safety

The Data and Safety Monitoring Plan (DSMP) outlined below will adhere to the protocol approved by Emory University. An IRB-approved written informed consent will be obtained from each participant at entry into the study; elements of informed consent will include: (a) having the participant review the study consent form; (b) having the investigator(s) or study staff meet with the participant to review the consent, confirm understanding, and answer any questions; and (c) once the investigator(s) or study staff are convinced that the protocol is understood and that there is agreement to participate, having the consent signed. The principal investigator (PI) will review all data collection documents weekly for completeness and accuracy of the data as well as protocol compliance. The PI will review this protocol on a continuing basis for participant safety and include the results of the review in annual progress reports submitted to the IRB and the NIH.

Patient Monitoring will be performed by the P.I., Co-Investigators, the Project Coordinator and medical staff present during the experimental manipulation. Also, H&P is required per the GCTSA protocol.

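### Free improvement: no Aim 2 analysis is specified to adjust for the participant's own resting blood pressure or pre-task biomarker value, although both are collected

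*Combined protocol and SAP*

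**What the plan says.** All references are to the combined protocol and SAP.

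- **Section III.E.viii (Inflammatory and Blood Pressure Reactivity):** "Blood pressure reactivity will be a change (or delta) score", formed as the mean over the recall task minus the mean over rest. Blood pressure is also read through rest and recovery. Inflammatory markers are drawn just before the task and at 45 and 90 minutes after it. So a pre-task value exists for every Aim 2 outcome.
- **Section VIII.B (Main Outcome Analyses):** each biomarker and blood pressure is analysed by a 2X3 ANOVA of condition by period (rest, stress, recovery), "also controlling for the relevant covariates". Those covariates are not named. Rest is a level of the outcome.
- **Section III.E.vi (Covariates):** lists behavioural, socio-economic, psychosocial and comorbidity items, and "demographics such as age, sex, and body mass index". Neither resting blood pressure nor a pre-task biomarker value is on the list.
- **Section VIII.A (Exploratory Analyses):** adjustment is to be considered for demographic, clinical or behavioural variables that turn out to differ significantly.
- **Section VIII.C (Statistical Power), Aim 2:** "If we just consider the two study groups (intervention and control" groups), the plan claims "we would achieve power of .80 to detect a medium effect (.25") "at $\alpha=.05$ with a sample of just 64 participants".

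**The concern.** The comparison between the two recall conditions is the randomised answer to the second hypothesis. It is also the Aim 2 effect size that the study exists to supply for a larger one, so the precision of that estimate matters whether or not significance is a goal.

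The plan offers two kinds of condition contrast, and both handle the resting value inefficiently:

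- The delta score, and any condition-by-time contrast against rest, subtract the resting value with a slope fixed at 1. If the regression slope of the recall value on the resting value is below 1, this over-corrects and adds noise.
- The condition main effect averages all three periods. Rest precedes the manipulation, so including it dilutes the effect and lets a chance difference at rest into the estimate.

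Participants run from no CKD diagnosis to stage 4, so a wide spread of resting values is plausible, and the plan describes no stratification of the randomisation.

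**Working it through.** **The plan's own figure.** For two equal groups f = 0.25 is d = 2 × 0.25 = 0.5. By noncentral t, two-sided 0.05, power is 0.50 with 64 in total (32 per arm), 0.80 with 64 per arm (128 in total), and 0.70 with the planned 100 in total. The stated 0.80 therefore matches 64 per group, not 64 participants. That is a separate matter. What counts here is that the figure uses neither a resting value nor a rest-to-recall correlation, so it says nothing about how the baseline is to be used.

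**Inputs.**
- From the documents: 100 participants, equal chance of either condition, so about 50 per arm.
- Assumed, because the documents are silent: equal SD at rest and recall (set to 1), rest-to-recall correlation r = 0.5 to 0.9, two-sided testing at 0.05, no dropout.

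**Precision of the change contrast.**
- Variance per participant of the change score: 2(1 − r).
- Residual variance after adjusting for the resting value: 1 − r².
- Ratio, adjusted to change score: (1 − r²) / [2(1 − r)] = (1 + r)/2.

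**Effect of a resting imbalance.** With 50 per arm the standard error of the resting difference is √(2/50) = 0.20 SD. Given a one-standard-error imbalance:
- the change contrast is shifted by −(1 − r) × 0.20;
- the 2X3 condition main effect is shifted by +(1 + 2r)/3 × 0.20, taking correlation r between every pair of periods;
- the adjusted contrast is not shifted.

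| r | Change variance | Adjusted variance | Ratio | Shift, change contrast (SD) | Shift, main effect (SD) |
|---|---|---|---|---|---|
| 0.5 | 1.00 | 0.75 | 0.75 | −0.10 | +0.13 |
| 0.6 | 0.80 | 0.64 | 0.80 | −0.08 | +0.15 |
| 0.7 | 0.60 | 0.51 | 0.85 | −0.06 | +0.16 |
| 0.8 | 0.40 | 0.36 | 0.90 | −0.04 | +0.17 |
| 0.9 | 0.20 | 0.19 | 0.95 | −0.02 | +0.19 |

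A simulation of 20,000 trials with 50 per arm gave variance ratios of 0.75, 0.86 and 0.91 at r = 0.5, 0.7 and 0.8. The slope of the adjusted estimate on the imbalance was about zero.

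**Dilution of the main effect.** An effect of 0.40 SD at stress and recovery and zero at rest averages to (0 + 0.40 + 0.40)/3 = 0.27 SD. The simulation gave the same value.

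**Power, for scale only.** For a true difference of 0.4 SD at recall, a two-group test on the delta compared with the baseline-adjusted test gives 51% and 63% (r = 0.5), 60% and 70% (0.6), 73% and 79% (0.7), 88% and 91% (0.8), and 99% for both (0.9). These describe a two-group test on the delta, not the planned ANOVA.

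**Unequal spread.** Let k = SD(recall)/SD(rest). The change variance is k² + 1 − 2rk, the adjusted variance is k²(1 − r²), and the slope is rk.
- r = 0.5, k = 1.2: 1.08/1.24 = 0.87.
- r = 0.8, k = 1.1: 0.4356/0.45 = 0.97.
- r = 0.8, k = 1.25: slope 1, and 0.5625/0.5625 = 1.00, so no gain.

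**The case against.** Several points on the other side stand.

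- **The plan does not rule adjustment out.** The covariates in VIII.B are undefined, the list in III.E.vi is worded as examples, and VIII.A leaves later adjustment open. A reader might infer that the plan excludes baseline adjustment. The documents support only that none is specified.
- **The resting value is not ignored.** A reader might infer that the change score is biased, or that it passes a resting imbalance straight through. Under randomisation it is unbiased on average. It removes the imbalance by subtraction and, with equal SDs, overshoots by the fraction 1 − r. Its standard error already contains that chance error, so lost precision and conditional shift are largely one loss seen twice. With equal SDs and r above 0.5, the change score is still more precise than the recall value alone.
- **A correlation below 1 does not by itself put the slope below 1.** The slope also depends on the ratio of the SDs, and neither SD is in the documents.
- **The gain may be small.** The blood pressure values are means of several readings in one session, so a high correlation is plausible. No correlation is available for the biomarkers either.
- **The delta is defined as a measure and is never assigned to a model.** The power comparison above is therefore not the power of any test the plan specifies, and section VIII.C disclaims conventional power as a goal.

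None of this argues for leaving the baseline out. In large-sample terms the adjusted variance is never above the change-score variance, and the dilution of the condition main effect does not depend on r.

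**Conclusion.** The point holds as a free improvement; it does not show that the planned analysis is invalid. No Aim 2 analysis is specified to adjust for the participant's own pre-task value, although that value is collected for every outcome. With equal SDs, 50 per arm and r from 0.5 to 0.9, adjustment brings the variance of the change contrast to 0.75 to 0.95 of its present value. The benefit falls towards nil as r × SD(recall)/SD(rest) approaches 1. Under the same assumptions, a one-standard-error resting imbalance shifts the change contrast by 0.02 to 0.10 SD against the direction of the imbalance, and the condition main effect by 0.13 to 0.19 SD with it. The main effect also shrinks by one third when the manipulation acts only after rest. That last result is arithmetic on the design and needs no assumed correlation.

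**What to change.** In VIII.B, name the participant's own pre-task value as a covariate and take only the post-baseline periods as outcomes:

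- **Blood pressure:** recall and recovery mean SBP and DBP, each with its own resting mean as covariate.
- **Biomarkers:** the 45- and 90-minute values, with the pre-task value of the same marker as covariate.
- **Model:** one repeated-measures model per outcome with condition, time and condition-by-time. This keeps recovery and the interaction the plan wants, and takes rest out of the condition effect.

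The delta score in III.E.viii may stay. Regressing it on arm plus the resting mean gives the same arm coefficient as regressing the recall mean on arm plus the resting mean. Add the pre-task values to the list in III.E.vi so that the choice is fixed before the data are seen.

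The cost is a sentence or two of text and about one degree of freedom per model. There are no added participants, samples or procedures.
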